- 16. Nail Psoriasis Severity Index (NAPSI) will be performed on the target finger nail identified at baseline and be followed for duration of the study (Section 7.3.4).

1. Screening visit occurs within 28 (+10) days prior to Baseline (Day 1) visit.

- 17. Subject completed questionnaires include: Patient's Global Assessment of Arthritis (VAS), Patient's Global Assessment of Arthritis Pain (VAS), Health Assessment Questionnaire-Disability Index (HAQ-DI), Short-Form-36 Health Survey (Version 2, Acute) (SF-36), EuroQol 5 Dimensions (EQ5D) and The work productivity and Activity Impairment Psoriatic Arthritis Questionnaire (WPAI-PsA). All patient reported outcomes should be completed prior to any other assessments made at each visit.
- 18. If a subject discontinues from or completes the study with abnormalities in hematology or clinical chemistry results (as defined in Section 6.3.2), or a subject discontinues from study due to an adverse event, a follow-up visit must be performed after the Early Termination study visit within 28 days (+14 days) of last dose of study treatment. In addition, all subjects who complete the study must have a follow-up visit within 28 days (+14 days) of end of study visit.
- 19. Testings that are to be done in central lab: hematology, HbA1c, Lymphocyte subset analysis (FACS), Chemistry panel, Lipid Panel, Urinalysis, C-Reactive Protein (CRP), HIV serology, HBsAg, HBcAb, HCV Ab, Prothrombin time (INR), Rheumatoid Factor (RF), QuantiFERON-TB Gold, FSH testing if needed.
- 20. Confirm and document that contraception, if assigned, is used consistently and correctly.
- 21. Per amendment 3, all subjects will be asked at every study visit if they have any newly-developed risk factors for venous thromboembolism as described in Section 7.5.8.

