
Cases of gastrointestinal (GI) perforation were observed in RA subjects taking tofacitinib, often in the setting of diverticulitis. All affected subjects were taking concomitant non-steroidal anti-inflammatory drugs (NSAIDs) and/or corticosteroids that have been associated with an increased risk of GI tract injury. Isolated events of gastrointestinal perforation have also been reported in clinical trials in psoriasis and renal transplant subjects. These perforations were reported as diverticulitis or perforated diverticulum. In one report, the perforation occurred approximately two weeks after discontinuation of study therapy.

Interstitial lung disease (ILD), a complex co-morbidity in RA patients, has also been reported in RA patients receiving tofacitinib. While data from the RA development program do not identify a pulmonary toxicity for tofacitinib, an increased risk of ILD was observed in Asian RA patients as compared to non-Asian RA patients.

In the PsA development program, the serious infection rate was similar between tofacitinib doses, as well as between tofacitinib and adalimumab, and similar to the RA and PsO development programs.

The incidence rate of malignancy for the PsA program is within range of those observed in the RA and PsO programs. Rates in the RA and PsO long term extension (LTE) studies have not changed over time. The incidence rates for malignancies (excluding non-melanoma skin cancer, NMSC) in tofacitinib treated PsA subjects were found to be within the range of those that have been reported in the published PsA literature (including LTE trials) and comparable to published rates for other PsA approved therapies. The incidence rate for NMSC for the PsA program is within range of those observed in the RA and PsO programs.

Based on nonclinical data, there is a potential risk for teratogenicity with tofacitinib. A more detailed discussion of tofacitinib safety can be found in the Investigator's Brochure.

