### 4.1. Inclusion Criteria

Subjects must meet all of the following inclusion criteria to be eligible for enrollment into the study:

- 1. Evidence of a personally signed and dated informed consent document indicating that the subject (or a legally acceptable representative) has been informed of all pertinent aspects of the study.
- 2. Willing and able to comply with scheduled visits, treatment plan, laboratory tests, and other study procedures.
- 3. Female subjects of childbearing potential and at risk for pregnancy must agree to use a highly effective method of contraception throughout the study and for at least 28 days after the last dose of assigned treatment.

Female subjects of nonchildbearing potential must meet at least one of the following criteria:

- Have undergone a documented hysterectomy and/or bilateral oophorectomy;
- Have medically confirmed ovarian failure;
- Achieved post-menopausal status, defined as: cessation of regular menses for at least 12 consecutive months with no alternative pathological or physiological cause; status may be confirmed by having a serum follicle stimulating hormone (FSH) level within the laboratory's reference range for postmenopausal females.

All other female subjects (including female subjects with tubal ligations) are considered to be of childbearing potential.

- 4. The subject has signs and symptoms consistent with the diagnosis of PsA for at least 6 months and fulfills ClASsification criteria for Psoriatic ARthritis (CASPAR) Criteria at screening and has evidence of active arthritis based upon number of tender/painful and swollen joints detailed in Section 4.1.1 below.
- 5. Ongoing treatment with a stable dose of a csDMARD (eg, methotrexate or sulfasalazine) (Section 4.1.2 below).
- 6. Meet all other eligibility criteria described in Sections 4.2, 4.3 and 4.4 below.

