#### 6.2.8. Follow-up Visit

**Subjects are required to fast for at least 9 hours prior to the visit.** Blood collection may be taken up to 48 hours following this visit as necessary to ensure samples are collected in a fasted state.

If a subject discontinues from or completes the study with abnormalities in hematology or clinical chemistry results which meet criteria as defined in Section 6.3.2, or a subject discontinues from the study due to an adverse event, a follow-up visit must be performed after the Early Termination study visit and at least 28 calendar days and up to 42 calendar days after last dose of study treatment. In addition, subjects who complete this study will have a follow-up visit at least 28 calendar days and up to 42 calendar days after the last administration of investigational product. The following procedures will be performed:

- Laboratory testing: Hematology, Chemistry Panel; Lipid Panel (fasting), Urine Pregnancy Test (for women of childbearing potential only);
- Risk factor check for venous thromboembolism (see Section 7.5.8);
- Contraception check: Confirm and document that proper contraception is being used;
- Adverse event reporting and concomitant medication use.

If abnormalities in hematology or clinical chemistry results are still observed at the follow-up visit, the subject must continue to be followed until the laboratory abnormality stabilizes or returns to baseline levels as approved by the Sponsor.

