## 8.1.4. Time Period for Collecting AE/SAE Information

The time period for actively eliciting and collecting AEs and SAEs ("active collection period") for each subject begins from the time the subject provides informed consent, which is obtained before the subject's participation in the study (ie, before undergoing any study-related procedure and/or receiving investigational product), through and including a minimum of 28 calendar days after the last administration of the investigational product.

For subjects who are screen failures, the active collection period ends when screen failure status is determined.

Medical occurrences that begin before the start of study intervention but after obtaining informed consent will be recorded on the Medical History/Current Medical Conditions section of the case report form (CRF), not the AE section.

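### AE collection must run to 28 days after last dose for every subject, but those who leave early without an adverse event or a qualifying laboratory finding have no scheduled contact after Early Termination to detect new events

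*Protocol*

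**What the plan says.** Protocol Section 8.1.4 sets the period for actively eliciting AEs and SAEs. It applies "for each subject begins from the time the subject provides informed consent" and runs "through and including a minimum of 28 calendar days after the last administration of the investigational product". The only earlier end it allows is screen failure.

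The follow-up visit is conditional. Section 6.2.8 gives three triggers:

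- leaving or completing with "abnormalities in hematology or clinical chemistry results which meet criteria as defined in Section 6.3.2";
- discontinuing for an adverse event ("or a subject discontinues from the study due to an adverse event, a follow-up visit must be performed after the Early Termination study visit");
- completion: "subjects who complete this study will have a follow-up visit at least 28 calendar days and up to 42 calendar days" after the last dose.

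Footnote 18 of the Schedule of Activities has the same triggers; for completers it reads "all subjects who complete the study must have a follow-up visit within 28 days (+14 days) of end of study visit". Section 6.3 repeats the AE and laboratory triggers for withdrawals, and the closing paragraph of Section 6.3.2 repeats the laboratory trigger. The text under Table 6 (Section 7.5.7) adds one more group: anyone with clinically significant laboratory findings at the final assessment. Section 4.6.4 likewise treats the follow-up visit as one that may not be required.

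**The concern.** The collection rule covers every dosed subject, while the visit rule covers only some of them. The protocol itself names the exits that fall between the two:

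- rescue medication beyond 10 consecutive days, compliance below 80% over two consecutive visit periods, and interruption beyond 14 days (Section 6.3.2);
- insufficient response, or no longer wishing to take part (Section 6.3);
- COVID-19 logistics, recorded under the category Other (Section 7.7).

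A site that follows the visit schedule exactly makes no planned contact with these subjects after Early Termination to ask about new events.

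The protocol treats the weeks after the last dose as relevant. Among gastrointestinal perforations seen in other indications, it notes: "In one report, the perforation occurred approximately two weeks after discontinuation of study therapy". It also requires contraception "for at least 28 days after the last dose of assigned treatment". Comparing safety with placebo is a primary objective. SAP Section 3.5.1 attributes events to the treatment period whether they occur on or off treatment, so post-dose events count in the AE tables. If the chance of recording them depends on why a subject left, ascertainment is not uniform across subjects.

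**Working it through.** The plan gives no figure to reproduce here. The check compares the sections, then applies two short calculations.

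**1. Who has a scheduled contact near the end of the 28-day period**

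| Reason for leaving | Follow-up visit required? | Source (Protocol) |
|---|---|---|
| Completed the study | Yes | 6.2.8; footnote 18 |
| Adverse event | Yes | 6.2.8; footnote 18; 6.3 |
| Section 6.3.2 laboratory abnormality | Yes | 6.2.8; footnote 18; 6.3; 6.3.2 |
| Other clinically significant laboratory finding at final assessment | Yes | text under Table 6 |
| Rescue, non-compliance, non-medical interruption, insufficient response, own choice, COVID-19 logistics | No | no section provides one |

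**2. Days without scheduled contact**

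Let d be the number of days from last dose to the Early Termination visit. The documents do not fix d. Uncovered days = 28 − d.

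- d = 0: 28 − 0 = 28 days
- d = 7: 28 − 7 = 21 days
- d = 14: 28 − 14 = 14 days

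Under Section 6.2.8 a completer is seen 28 to 42 days after the last dose, so 0 days are uncovered.

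**3. Timing for subjects who do have the visit**

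Section 6.2.8 gives 28 to 42 days after the last dose. Footnote 18 gives 28 (+14) days, counted for completers from the end-of-study visit. Sections 6.3 and 6.3.2 and the text under Table 6 give 28 ± 7 days, which is day 21 to day 35. A visit on day 21 would fall 28 − 21 = 7 days before the collection period ends.

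**4. Size of the affected group (assumption)**

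No dropout rate is stated for this trial. Section 1.2.2 gives Month 3 completion in two earlier PsA studies:

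- A3921091: (422 − 406)/422 = 16/422 = 3.8%; 204 × 16/422 = 7.7, about 8 subjects
- A3921125: (395 − 364)/395 = 31/395 = 7.8%; 204 × 31/395 = 16.0, about 16 subjects

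These are all-reason figures to Month 3. Leavers without an AE or qualifying laboratory finding are an unknown part of them. Leavers between Month 3 and Month 6 would add to the count.

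**The case against.** The strongest reply is that Section 8.1.4 is itself a binding duty and Section 8.1.2 requires each subject to be questioned about AEs, so what is missing is a named contact and not the obligation. A site could comply by telephone. That is fair as far as it goes. But the protocol states who must have the follow-up visit, and a site working from that list has no prompt to call anyone else.

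Other provisions reach beyond Early Termination, and a reader who infers that these subjects have no safety follow-up at all would be wrong:

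- Section 6.3 asks sites to follow unresolved AEs and to try to document outcome.
- Section 6.2.7 has laboratory abnormalities reviewed at the final visit, and Section 6.3 asks for follow-up of clinically significant treatment-emergent abnormalities.
- Section 8.1.4.1 covers SAEs that the investigator learns of later.

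These deal with events already open, findings already known, or SAEs that happen to come to notice. None schedules a contact to detect new events.

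Three stronger readings are tempting and are not supported:

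- That these subjects have no contact at all in the 28 days after last dose. The Early Termination visit may fall within that period. For a subject withdrawn for an interruption beyond 14 days, a visit made after the criterion is met already lies more than 14 days after the last dose.
- That a much larger group is affected. The documents' highest non-completion figure, 141/792 = 17.8%, comes from A3921046, a rheumatoid arthritis study, and covers that whole study. Any split of leavers by reason would be a guess.
- That AE rates are biased between arms. No section gives reasons for leaving by arm. The AE summaries are described as exploratory, and Tier-2 events carry no p-values (SAP Sections 5.2.3 and 6.6.1).

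The six-week restriction on live vaccines does not strengthen the case, because a contact at day 28 would not cover it either.

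**Conclusion.** The mismatch is real and stands in the current text. Collection is required for every subject, while the visit that would carry it out is limited by reason for leaving. For the remaining early leavers, 28 minus d days have no scheduled contact to detect new events. That is 14 to 28 days for d between 0 and 14, a range taken for illustration.

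The number of subjects is modest and uncertain. About 8 to 16 early leavers by Month 3 is an all-reason figure that assumes this trial behaves like the two earlier PsA studies. The affected group is an unknown part of it, plus those who leave later.

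Post-dose AE capture depends on the reason for leaving. Whether that differs between arms cannot be determined from the documents, and the effect on the AE comparison is probably small. The primary efficacy analysis is not touched. The point is worth correcting because two parts of the protocol disagree about who is followed and the correction is cheap.

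**What to change.** Reconcile Section 6.2.8, footnote 18 of the Schedule of Activities, Section 6.3, the closing paragraph of Section 6.3.2 and the text under Table 6 with Section 8.1.4. The reconciled text should do two things:

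- State how AE/SAE data are elicited at or after day 28 post-dose for every subject who took at least one dose, whatever the reason for stopping. Subjects who withdraw consent for further information remain exempt under Section 6.3. As data collection, a telephone AE/SAE contact would be enough.
- Remove the conflict between the 28 ± 7 day timing, the 28 to 42 day timing and the different starting points, so that no stated timing lets the contact fall before the Section 8.1.4 period ends.

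The cost is a short edit in five places and a small number of extra calls: no more than about 8 to 16 for leavers by Month 3, even if every one of them were affected, plus some for later leavers. Subjects who are lost to follow-up would still be missed.

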#### 6.3. Subject Withdrawal

Subjects may withdraw from the study at any time at their own request, or they may be withdrawn at any time at the discretion of the investigator or sponsor for safety (see also the Withdrawal From the Study Due to Adverse Events section) or behavioral reasons, or the inability of the subject to comply with the protocol-required schedule of study visits or procedures at a given study site.

If a subject does not return for a scheduled visit, every effort should be made to contact the subject. In any circumstance, every effort should be made to document subject outcome, if possible. The investigator should inquire about the reason for withdrawal, request the subject to return all unused investigational product(s), request the subject return for a final visit and follow-up with the subject regarding any unresolved adverse events (AEs).

If the subject withdraws from the study, and also withdraws consent for disclosure of future information, no further evaluations should be performed, and no additional data should be collected. The sponsor may retain and continue to use any data collected before such withdrawal of consent. Withdrawal due to adverse event should be distinguished from withdrawal due to insufficient response according to the definition of adverse event noted in Section 8.2.1. Withdrawal due to a subject being no longer willing to participate in the study should be distinguished from withdrawal due to "lost to follow-up" (LTFU). Every effort should be made to identify and contact subjects who are potentially LTFU. A subject should not be considered a withdrawal due to LTFU until at least 3 attempts to contact the subject by multiple methods have been unsuccessful. All methods of attempted contact with the subject must be clearly documented (dated and initialed) in the subject's source documents and recorded on appropriate CRF page. All potential LTFU subjects must be discussed with the Pfizer study team or designee prior to assigning LTFU status. If a subject discontinues from the study due to an adverse event (AE) or any abnormality in hematology or clinical chemistry results which meet the criteria as defined in Section 6.3.2, a follow-up visit must be performed within 28 days ( $\pm$ 7 days) of last dose of study treatment. The investigator must determine and document the primary reason for subject withdrawal.

If a subject has any clinically significant, treatment-emergent, abnormalities at the conclusion of the study, the Sponsor (or designated representative) should be notified and every effort should be made to arrange follow-up evaluations at appropriate intervals to document the course of the abnormality. All abnormal laboratory events of clinical significance should be followed until the laboratory values have returned to normal or baseline levels.

# 6.3.1. Monitoring Criteria

The following laboratory abnormalities require prompt retesting, ideally within one week:

- Any single hemoglobin value that drops  $\geq 2 \text{ g/dL}$  (or  $\geq 20 \text{ g/L}$ ) below baseline;
- Absolute neutrophil count  $<1.2 \times 10^{9}/L$  ( $<1200/mm^{3}$ );
- Absolute lymphocyte counts  $<0.5 \times 10^9/L$  ( $<500/mm^3$ );
- Platelet count  $<100 \text{ x } 10^9/\text{L} (<100,000/\text{mm}^3);$
- Serum creatinine increase >50% OR an absolute increase in serum creatinine >0.5 mg/dL (or 44 μmol/l) over the average of the screening and baseline values;
- Any creatine kinase (CK) >5x ULN (repeat laboratory testing should also include cardiac troponin).

If the abnormality is confirmed after re-test, follow-up should be discussed with the Sponsor and frequency of monitoring increased. Confirmation should be done based upon central laboratory results, but local laboratory results will be acceptable, particularly if these may be done more promptly.

In case of potential DILI, repeat laboratory tests should be taken within 48 hours of awareness. See Section 8.4.2 Potential Cases of Drug-Induced Liver Injury.

#### 6.3.2. Discontinuation Criteria

Study drug will be discontinued and the subject withdrawn from the study in the event of any of the following:

- Requirement of rescue medication for more than 10 consecutive days;
- Subjects who are <80% compliant with dosage regimen for any two consecutive visit periods should be withdrawn from the study;
- Subjects interrupting study drug for more than 14 consecutive days;
- Serious infections defined as any infection (viral, bacterial, or fungal) requiring parenteral antimicrobial therapy or hospitalization for treatment, or meeting other criteria that require the infection to be classified as a serious adverse event (see Section 8.4.4);

- Two sequential absolute neutrophil counts  $<1.0 \times 10^9/L$  ( $<1000/mm^3$ );
- Two sequential hemoglobin values <8.0 g/dL (80 g/L) or decreases of >30% from baseline value;
- Two sequential absolute lymphocyte counts  $<0.5 \times 10^9/L$  ( $<500/mm^3$ );
- Two sequential platelet counts  $<75 \times 10^9/L$  ( $<75,000/mm^3$ );
- Two sequential AST or ALT elevations ≥3 × ULN with at least one total bilirubin value ≥2 × ULNI;a
- Two sequential AST or ALT elevations ≥3 × ULN accompanied by signs or symptoms consistent with hepatic injury (eg, new onset elevated PT/INR);a
- Two sequential AST or ALT elevations >5 × ULN, regardless of total bilirubin or accompanying signs or symptoms;a
- Two sequential increases in serum creatinine >50% AND an absolute increase in serum creatinine >0.5 mg/dL (44 μmol/l) over the average of the screening and baseline values;
- Two sequential creatine kinase (CK) elevations >10 × ULN, unless the causality is known not to be medically serious (eg, exercise or trauma induced);
- A confirmed positive urine pregnancy test in a woman of childbearing potential;
- Any opportunistic infections considered significant by the investigator or the Sponsor;
- Confirmed venous thromboembolism;
- Other serious or severe adverse events, in the opinion of the investigator or Sponsor. Whenever possible, the investigator should consult with a member of the Pfizer study team before discontinuation of the subject.

If a subject discontinues from the study due to abnormalities in hematology or clinical chemistry parameters which meet criteria as defined in this section, a follow-up visit must be performed within 28 days ( $\pm$ 7 days) of last dose of study treatment. For a confirmed increase in serum creatinine of >50% and >0.5 mg/dL above the average of screening and baseline, laboratory values will be followed with retesting until the creatinine elevation has stabilized (ie, stopped increasing) over at least 3 consecutive tests obtained monthly.

a. In each case, there is a need for additional investigations, such as review of ethanol, recreational drug and dietary supplement consumption; testing for acute hepatitis A, B or C infection and biliary tract imaging should be promptly discussed with the Sponsor or designee.

### 7. ASSESSMENTS

Every effort should be made to ensure that the protocol required tests and procedures are completed as described. However, it is anticipated that from time to time there may be circumstances, outside of the control of the investigator, which may make it unfeasible to perform the test. In these cases the investigator will take all steps necessary to ensure the safety and well being of the subject. When a protocol required test cannot be performed the investigator will document the reason for this and any corrective and preventive actions that he/she has taken to ensure that normal processes are adhered to as soon as possible. Single missed assessments, if justified, would not be considered as non-adherence to protocol; reason for missed evaluation must be documented. Two or more consecutively missed assessments for any endpoint would be considered non-adherence and be reported. The study team will be informed of these incidents in a timely manner.

